2.4.3 Elimination criteria

- Nausea and/or vomiting
- Feeling faint or faint
- Intolerance to oral anhydrous glucose load
- Withdrawal of consent under information

2.5 Variables

2.5.1 Independent variable

- PREDIcted M (PREDIM)

2.5.2 Dependent variables

- Insulin sensitivity
- McAuley index
- Belfiore index
- Cederholm index
- Avignon index
- Matsuda index
- Gutt index
- Stumvoll index
- HOMA-IR index
- ISI index
- Raynaud index
- QUICKI index
- FIRI index
- Bennett index
- TyG index

2.5.3 Intervening variables

- Follicular phase of a woman's menstrual cycle.

2.6 Study groups and administration of the intervention

- 25 healthy patients will be tested for oral glucose tolerance **test**.

2.7 Measurement and evaluation procedures

2.7.1 Clinical determinations

Age:

Patients from 30 to 60 years old will be included volunteers who agree to participate and sign informed consent, residents of the metropolitan area of Guadalajara.

Gender:

It will be registered as M (Male) and F (Female).

BMI:

It will be obtained from the division between the weight in kilograms and the height in square meters (kg/m²).

Waist circumference:

It will be measured with a tape measure of flexible material graduated in centimeters (cm), with the subject in a standing position, for which, the tape will be placed in a plane parallel to the horizontal and without clothing at the level of the measurement. The tape will be placed at the level of the middle zone between the costal border and the iliac crests at the end of a normal expiration

Weight:

Measurements will be recorded in kilograms (kg) using a stationary TANITA® electrical bioimpedance scale. It will be measured with the participant in a standing position and wearing light clothing, without footwear and with the bladder evacuated before the measurement.

Blood pressure:

Measurements will be recorded in millimeters of mercury (mmHg) using the OMRON HEM 907 XL digital sphygmomanometer. For this, the subject will be placed in a sedative position and after 15 min of rest, a bracelet will be adjusted 3 cm above the fold of the elbow of the left arm. 3 intakes and an average blood pressure will be taken.

2.7.2 Laboratory determinations

For serum glucose measurements (fasting and PTOG at 3 h), secretion and sensitivity to insulin, total cholesterol, triglycerides, creatinine and uric acid, a catheter will be placed for the venous blood sample, the measurements will be made by simple enzymatic-colorimetric techniques with an automated clinical chemistry analysis equipment XL-100Erba® brand, which will be routinely calibrated according to the general laboratory log and will be operated by a single certified chemist assigned to this study.

2.7.3 Calculations

Insulin sensitivity:

it will be calculated with the indices:

Index	Formula
PREDICTed M (PREDIM)	$A + B \times \log_e(OGIS) + C \times \log_e(IMC) + D \times \log_e(2hGlu) + \log_e(INSf)$
Matsuda	$\frac{10000}{\sqrt{(G_0 I_0)(G_{mean} I_{mean})}}$
McAuley	$e[2.63 - 0.28 \ln(I_0) - 0.31 \ln(TG_0)]$
Belfiore	$\frac{2}{ISI_{Belfiore}} = \frac{G_s}{G_N} \times \frac{I_s}{I_N} + 1$
Cederholm	$\frac{75000 + (G_0 - G_{120}) \times 1.15 \times 180 \times 0.19 \times \text{body weight}}{120 \times Glu_{mean} \times \log(Ins_{mean})}$
Avignon	$Sib = \frac{10^8}{I_0 \left(\frac{\mu U}{l}\right) \times G_0 \left(\frac{mmol}{l}\right) \times VD}$ $Si2h = \frac{10^8}{I_{120}(\mu U/l) \times G_{120}(mmol/l) \times VD}$ $SiM = \frac{(0.137 \times Sib) + Si2h}{2}$
Stumvoll	$0.156 - 0.0000459 \times I_{120}[pmol/l] - 0.000321 \times I_0[pmol/l] - 0.00541 \times G_{120}(mmol/l)$
Gutt	$\frac{75000 + (G_0 - G_{120})(mg/dl) \times 0.10 \times PC}{120 \times G_{mean}(mmol/l) \times \log[I_{mean}](\mu U/l)}$
HOMA-IR	$\frac{(Fasting\ insulin)(\mu U/ml) \times (Fasting\ glucose)(mmol/l)}{22.5}$
ISI	$\frac{10000}{(fasting\ insulin) \times (fasting\ glucose)}$
Raynaud	$\frac{40}{fasting\ insulin}$
QUICKI	$\frac{1}{\log(fasting\ insulin)(\mu U/ml) + \log(fasting\ glucose)(mg/dl)}$

FIRI	$\frac{(fasting\ insulin) \times (fasting\ glucose)}{25}$
Bennett	$\frac{1}{\log(fasting\ insulin) \times \log(fasting\ glucose)}$
TyG	$\frac{Ln(fasting\ triglycerides)(mg/dl) \times (fasting\ glucose)(mg/dl)}{2}$

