1. INTRODUCTION

The term insulin sensitivity-insensitivity is referred to for the first time in 1936 by Himsworth, who took a background from redactions dating back to 100-200 BC. of C. Insulin sensitivity is defined as its effectiveness in lowering blood glucose by promoting glucose uptake by muscle and adipose tissue cells, increasing hepatic glycogen production, and reducing hepatic glucose production.^{2,3} Therefore, insulin resistance is a pathophysiological phenomenon in which, for a given concentration of this hormone, an adequate reduction in blood glucose levels is not achieved, which results in the event for which the individual is able to maintain a normal tolerance to glucose over finite periods and comes intolerance carbohydrates and at consequence, the occurrence of various diseases as diabetes mellitus, the arterial hypertension and central obesity.^{4,5}

Early diagnosis of insulin resistance along with timely intervention can prevent the onset of these conditions. He currently has several methods for measuring sensitivity, within which the most accurate and precise, considered the "gold standard" is the clamp to hyperglucemic-hyperinsulinemic. However, they are expensive and time-consuming and personnel-intensive, so they are limited for use in specialized experimental clinical research centers and not as a diagnostic means. This has led to the search and development of indices that allow to quantify insulin sensitivity/resistance, classified according to the data used for the calculation in:⁷

1. Indices calculated using fasting plasma concentrations of insulin, glucose and triglycerides: HOMA-IR (Homeostatic Evaluation Model), Quantitative verification of insulin sensitivity (QUICKI), insulin sensitivity (ISI), Raynaud's, fasting insulin resistance (FIRI), Bennett, triglycerides and glucose (TyG).
2. Indices calculated using plasma insulin and glucose concentrations obtained over 120 min of a standard (75 g glucose) PTOG: Hyperglycemic-hyperinsulinemic clamp (CLAMP), McAuley, Belfiore, Cederholm, Avignon, Stumvoll, Gutt, Matsuda.

Recently, an index based on the oral glucose insulin sensitivity index (OGIS) in combination with anthropometric variables, called PREDIcted M (PREDIM), has been proposed; however, there is no evidence of its validation with respect to the various indices for the evaluation of insulin sensitivity, so the objective of this protocol is compare them with the afore mentioned indices.⁸

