2.4.2 Exclusion criteria

- Blood pressure >120/80 mmHg
- Glucose >100 mg/dL
- Glucose postprandial >140 mg/dL
- Cholesterol >200 mg/dL
- Triglycerides >150 mg/dL
- Smoking
- Women with polycystic ovary syndrome
- History of metabolic, cardiovascular, thyroid, renal, pancreatic and/or arterial hypertension disease
- Use of medications that modify insulin sensitivity (corticosteroids)
- Previous surgery or infection
- Symptoms of vomiting and/or excessive nausea

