3. STATISTIC ANALYSIS

Statistical analyses will be performed using SPSS statistical software (version 25). Values will be presented as measures of central tendency and dispersion, mean \pm standard deviation. Nominal variables in numbers and percentages. The Kolmogorov-Smirnov test will be performed to determine if the variables follow a normal distribution. Spearman correlation coefficients will be used to analyze the univariate relationship between index Predicted M (PREDIM) technique with various indices (McAuley, Belfiore, Cederholm, Avignon, Matsuda, Gutt, Stumvoll, HOMA-IR, ISI, Raynaud, QUICKI, FIRI, Bennett and TyG). A *P* value less than 0.05 will be considered significant.

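### As printed, the TyG formula logs triglycerides only and multiplies by unlogged glucose; followed literally, it changes the ranks behind the PREDIM–TyG correlation and the scale of the reported mean

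*Combined protocol and SAP*

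**What the plan says.** The formula table in Section 2.7.3 (Calculations) gives the TyG numerator as "Ln(fasting\ triglycerides)(mg/dl) \times (fasting\ glucose)(mg/dl") and divides the whole by 2. The Ln bracket encloses triglycerides alone, and glucose follows as a separate factor.

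In the same table the QUICKI denominator is "\log(fasting\ insulin)(\mu U/ml) + \log(fasting\ glucose)(mg/dl"), with a log written out for each variable. The Bennett row does the same.

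The Introduction names the index only as "triglycerides and glucose (TyG") and gives no formula. No other section defines it.

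Section 3 (Statistic analysis) states: "Spearman correlation coefficients will be used to analyze the univariate relationship between index Predicted M (PREDIM) technique with various indices". The list of indices ends with "HOMA-IR, ISI, Raynaud, QUICKI, FIRI, Bennett and TyG". Section 3 also plans to present values as mean ± standard deviation and sets the significance threshold at P below 0.05.

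**The concern.** Spearman's coefficient uses ranks only, so a monotone slip in a formula would do no harm. This one is not monotone. Ln(TG × G / 2) and Ln(TG × G) / 2 both increase in the product TG × G and rank participants identically. Ln(TG) × G / 2 compresses triglycerides and leaves glucose on its raw scale, so it can order the same people differently.

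Anyone who computes the row as printed therefore correlates PREDIM with differently ranked values, and reports a TyG mean and SD on another scale. By the formulas in Section 2.7.3, TyG is also the only one of the 14 comparators with no insulin term, while PREDIM contains fasting insulin. Its coefficient is thus the one that does not rest on a shared insulin measurement.

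**Working it through.** **The plan's own figure.** The plan states no number for TyG. Its only computed result is the sample size: 3 + 13.0 / 0.8517² = 20.92, and 20.92 × 1.2 = 25.1, given as 25. This reproduces, and TyG does not enter it.

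**Inputs from the documents.** Section 2.4.2 excludes "Glucose >100 mg/dL" and "Triglycerides >150 mg/dL", so eligible values reach at most 100 and 150 mg/dL. The TyG row prints mg/dl for both inputs.

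**Inputs assumed.** The documents give no mean, SD or correlation for glucose or triglycerides. I took glucose mean 80–90 and SD 5–10 mg/dL, triglyceride median 80–100 mg/dL with log-SD 0.25–0.50, and a correlation of 0 to 0.4 between them, truncated at the exclusion limits.

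**Step 1: a pair of eligible participants (no distribution needed).**

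| TG, G (mg/dL) | Ln(TG) × G / 2 | Ln(TG × G / 2) | Ln(TG × G) / 2 |
|---|---|---|---|
| 150, 70 | 5.011 × 35 = 175.4 | ln 5250 = 8.566 | ln 10500 / 2 = 4.63 |
| 50, 100 | 3.912 × 50 = 195.6 | ln 2500 = 7.824 | ln 5000 / 2 = 4.26 |

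The printed form puts the second participant higher. Both product forms put the first higher.

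**Step 2: relative weight, on one log scale.** Triple triglycerides from 50 to 150, or raise glucose from 75 to 100.
- Printed form: ln(5.011 / 3.912) = 0.25 for triglycerides; ln(100 / 75) = 0.29 for glucose.
- Product form: ln 3 = 1.10 for triglycerides; 0.29 for glucose.

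The printed form brings the two inputs close to parity. In the product form triglycerides count far more.

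**Step 3: simulated Spearman correlations, 60 combinations of the assumed inputs.**

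| Correlation | Printed form | Product inside the log |
|---|---|---|
| with glucose | 0.56–0.91 | 0.16–0.63 |
| with triglycerides | 0.48–0.87 | 0.92–0.99 |

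The two forms correlate with each other at 0.77 to 0.93. A separate check under assumed spreads gave about 0.76 to 0.94, which I use as the outer range.

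**Step 4: scale.** With glucose 87 ± 6 mg/dL and triglycerides of median 90 mg/dL and log-SD 0.35, the mean is about 193 as printed, about 8.2 for Ln(TG × G / 2) and about 4.5 for Ln(TG × G) / 2. Where the 2 sits changes the mean but not the ranks.

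**The case against.** The strongest reply is that this is notation only. HOMA-IR, ISI and FIRI in the same table use brackets merely to delimit variable names. TyG can be read as that pattern with Ln in front of the whole product, and an outer bracket may have been lost in typesetting. The calculation sheet may be correct. The documents also never print a reference TyG formula, so they cannot prove which form was meant. All of this stands as a limit on what can be claimed. It does not remove the problem: QUICKI and Bennett repeat the log for each variable, which favours the literal reading, and nothing elsewhere settles it.

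Two stronger readings are tempting, and the documents support neither.

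- A reader might infer that the printed index mostly ranks fasting glucose. That depends on spreads the plan does not give. Glucose led in the runs with an SD of 8 to 10 mg/dL. With an SD of 5 or 6 and a triglyceride log-SD of 0.35 or more, triglycerides still led. With glucose 87 ± 6 and log-SD 0.35 the two are nearly level: 0.68 for glucose and 0.70 for triglycerides when uncorrelated. Much more weight on glucose is shown; dominance is not.
- A reader might argue that the printed form is wrong because its ranks change between mg/dL and mmol/L. The row specifies mg/dl for both inputs, so that case does not arise when the row is followed.

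It is also fair to say that the effect on the PREDIM–TyG coefficient itself has not been estimated. It would need the joint distribution with PREDIM, which the documents do not supply.

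**Conclusion.** The point holds as a formula that needs correcting, not as proof of a wrong result. If the row is computed as printed, eligible participants can be put in reverse order; that follows from the algebra alone. The rest rests on assumed distributions: agreement between the two forms of about 0.76 to 0.94, a Spearman with glucose of roughly 0.5–0.9 instead of 0.15–0.6, and a mean near 190 instead of about 8.2.

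What would be affected is one of 14 planned Spearman coefficients and the TyG mean ± SD. The other 13 coefficients and the sample size are not. Whether any calculation actually used the literal form is unknown.

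**What to change.** Rewrite the TyG row in Section 2.7.3 with the whole product inside the log:

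Ln[fasting triglycerides (mg/dl) × fasting glucose (mg/dl) / 2]

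Show the position of the 2 explicitly, and have the sponsor confirm the form against the source it relies on, since the documents do not print one. Then check that the calculation sheet or SPSS syntax uses the same expression. A quick test is the output: values near 8 match this form, values near 4.5 mean the 2 divides the log, and values near 190 mean the literal row was used.

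The cost is one bracket in the table and one check. No new data are needed, because fasting glucose and triglycerides are already measured.

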2.7.4 Description of the study

Scrutiny visit

All patients will be scheduled at 8:00 AM with a minimum of 8 hours of fasting. The candidate volunteers will be provided with the information regarding the study, and the benefits to their health, the possible adverse effects, the objectives and the methodology that will be implemented will be indicated, with the purpose of submitting to the patient's consideration the signature of the consent under information to accept to participate. Once signed, the screening tests will be carried out according to the inclusion criteria, as well as capturing the clinical history and the complete physical examination. A venous blood sample will be taken for evaluation of clinical biochemical selection criteria, which include serum concentrations of: fasting glucose, lipid profile, creatinine and uric acid.

All participants who satisfactorily meet the selection criteria will be included in the intervention phase..

Baseline visit (Day 1)

The patient will be scheduled at 8:00 AM with a minimum of 8 hours of fasting. Weight, height, waist circumference and blood pressure will be taken. Subsequently, a catheter will be placed for the venous blood sample; an oral glucose tolerance and insulin sensitivity test will be performed, for which a 75 g dose of glucose dissolved in water will be administered orally. After the ingestion of the glucose solution, the venous blood will be taken at times 0, 30, 60, 90, 120, 150 and 180 minutes.

3. STATISTIC ANALYSIS

Statistical analyses will be performed using SPSS statistical software (version 25). Values will be presented as measures of central tendency and dispersion, mean \pm standard deviation. Nominal variables in numbers and percentages. The Kolmogorov-Smirnov test will be performed to determine if the variables follow a normal distribution. Spearman correlation coefficients will be used to analyze the univariate relationship between index Predicted M (PREDIM) technique with various indices (McAuley, Belfiore, Cederholm, Avignon, Matsuda, Gutt, Stumvoll, HOMA-IR, ISI, Raynaud, QUICKI, FIRI, Bennett and TyG). A *P* value less than 0.05 will be considered significant.

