2.3 Sample size

The sample size was calculated with the formula for simple correlation in a group ⁹:

$$n = 3 + \frac{K}{C^2}$$

	PREDIcted M (PREDIM)
	Insulin sensitivity
Confidence level	95 %
Statistical power	80 %
K (Z α + Z β)	13.0 ⁹
R	0.692 ⁸
C= 0.5 ln $\frac{1+r}{1-r}$	0.8517
N	20.92
n with 20 % losses	25

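### Section 3 reads 14 Spearman correlations by P<0.05 alone, although PREDIM shares fasting insulin with at least 10 comparators and four comparators must give the same result

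*Combined protocol and SAP*

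**What the plan says.** The Introduction motivates the study by saying of PREDIM that "there is no evidence of its validation with respect to the various indices for the evaluation of insulin sensitivity", and states that "the objective of this protocol is compare them with the afore mentioned indices". Section 3 gives the analysis: "Spearman correlation coefficients will be used to analyze the univariate relationship between index Predicted M (PREDIM) technique with various indices", the list being "McAuley, Belfiore, Cederholm, Avignon, Matsuda, Gutt, Stumvoll, HOMA-IR, ISI, Raynaud, QUICKI, FIRI, Bennett and TyG". The one rule for reading the results is that a P "value less than 0.05 will be considered significant". Section 3 plans no confidence interval, expected sign or minimum rho, and does not mention inputs common to PREDIM and its comparators. The value 0.692 in Section 2.3 serves only to size the study.

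Section 2.7.3 prints PREDIM as a function of OGIS, BMI, 2-hour glucose and fasting insulin. The last two terms read "D \times \log_e(2hGlu) + \log_e(INSf"). The constants A to D and the OGIS formula are not given, and the fasting-insulin term carries no coefficient.

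**The concern.** A test of rho = 0 asks whether two quantities are unrelated. When both are computed from the same fasting insulin value, some correlation is expected whether or not PREDIM carries any further information about insulin sensitivity. A small P value then answers a question of little interest.

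There is also a counting problem. Spearman's rho uses ranks only, so comparators that rank participants identically give the same result under different names. Followed as written, the plan can list up to 14 significant correlations without showing that four are one result, that one sets PREDIM against its own ingredient, or which of the rest rest on a common input. A reader could not separate concordance built into the formulas from concordance beyond them.

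**Working it through.** **1. Sample size (Section 2.3).** n = 3 + K/C², with K = 13.0 and C = 0.8517 as printed: 3 + 13.0/0.7254 = 20.92, which reproduces the stated figure. 20.92 × 1.2 = 25.1, against 25 stated on the line "n with 20 % losses". Below, n = 25 is full recruitment and n = 21 is the number before the loss allowance.

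**2. Shared inputs (Section 2.7.3, as printed).**

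| Input of PREDIM | Comparators that contain it |
|---|---|
| Fasting insulin | Matsuda, McAuley, Avignon, Stumvoll, HOMA-IR, ISI, Raynaud, QUICKI, FIRI, Bennett (10) |
| 2-hour glucose | Cederholm, Gutt, Avignon, Stumvoll (adds 2) |
| BMI, i.e. weight over height squared | Cederholm, through body weight |

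So 12 of 14 share fasting insulin or 2-hour glucose with PREDIM. TyG contains neither. Belfiore's terms are not defined. VD in Avignon and PC in Gutt are not defined there either and may also carry body weight. Overlap through OGIS cannot be counted. Ten is a minimum for fasting insulin, because mean-insulin terms may include the time-0 sample.

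**3. Rank equivalence.** Let x = fasting insulin × fasting glucose.
- HOMA-IR = x/22.5 and FIRI = x/25 increase in x.
- ISI = 10000/x decreases in x.
- QUICKI = 1/(log insulin + log glucose) = 1/log x decreases in x when x > 1.

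A change of glucose unit multiplies x by a constant and leaves ranks alone. The four therefore share one |rho| and one P value; in 2,000 simulated samples of 25 the largest spread in |rho| was 0. Distinct comparisons: 14 - 3 = 11 at most. If Belfiore's subscripted terms are fasting values divided by constants, it would be a fifth member and the count would be 10.

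Raynaud = 40/fasting insulin, a single PREDIM term. Under the spreads assumed in step 5, Raynaud and HOMA-IR have a median |rho| of about 0.98 with each other, so Raynaud and the HOMA-IR group are close to one comparison as well.

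**4. What P<0.05 requires.** Critical |rho| = t/√(n - 2 + t²), two-sided (sidedness is not stated).
- n = 25: t = 2.069, |rho| = 0.396, rho² = 0.157.
- n = 21: t = 2.093, |rho| = 0.433, rho² = 0.187.

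95% intervals at n = 25, on the Fisher z scale:

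| rho | z | Plain SE, 1/√22 = 0.213 | Bonett-Wright SE, √((1 + rho²/2)/22) |
|---|---|---|---|
| 0.396 | 0.419 | 0.00 to 0.68 | SE 0.221: -0.01 to 0.69 |
| 0.692 | 0.852 | 0.41 to 0.85 | SE 0.237: 0.37 to 0.87 |

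**5. Can overlap alone give significance? (illustration only)** All raw inputs were drawn independently, so any correlation comes from the shared term. Assumed log-scale SDs: fasting and mean insulin 0.45, fasting glucose 0.07, mean glucose 0.15, triglycerides 0.35. There were 4,000 samples per cell. The share of PREDIM's variance due to fasting insulin is an assumption and is varied. Percentage of samples with P<0.05 at n = 25:

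| Assumed share | HOMA-IR group | Matsuda | TyG |
|---|---|---|---|
| 0% | 5 | 4 | 5 |
| 10% | 29 | 17 | 5 |
| 20% | 56 | 29 | 5 |
| 30% | 76 | 42 | 5 |
| 50% | 97 | 65 | 5 |

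The mechanism is real, but its size depends on a share that the documents do not fix.

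**6. Sign.** With the fasting-insulin term read literally as printed (coefficient +1), and with assumed values for the other coefficients and spreads, HOMA-IR reaches P<0.05 at n = 21 in about 96 to 100% of such samples, and PREDIM rises with HOMA-IR. With negative weights the correlation is negative. A P-only rule would pass either direction.

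**The case against.** The strongest reply is that concordance with other indices is the declared aim, so overlap is part of what is being described. Fasting insulin is itself a marker of insulin sensitivity, so correlation through it is not mere artefact. Section 3 plans correlation coefficients, which are effect estimates, and then defines significance in the usual way. The formulas are printed, so a careful reader can see most of the overlap. All of this stands, and it lowers the severity.

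Two stronger readings are tempting. A reader might infer that the plan treats P<0.05 as proof that PREDIM is valid; no passage says so. A reader might also infer that the significant correlations will be largely artefact. The documents do not support that: A to D, the OGIS formula and the fasting-insulin coefficient are not given, and independent inputs are an unrealistic extreme. The percentages in step 5 show that overlap can produce significance, not how often it will here.

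The reply does not remove the algebra. Four comparators give one result and Raynaud is one of PREDIM's own terms, whatever the coefficients are. Nor does printing rho supply its precision or a rule for reading it.

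**Conclusion.** The point holds as one of interpretation and reporting, of minor to moderate weight. Firm from the printed formulas: fasting insulin in at least 10 of 14 comparators, 12 of 14 sharing fasting insulin or 2-hour glucose, four rank-equivalent indices, and at most 11 distinct comparisons. Also firm, given n = 25 and a two-sided test: |rho| of about 0.40 suffices for significance, and a result at that margin is compatible with almost no association.

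Not established: how much of any observed correlation will come from shared inputs. That rests on assumed values, and the illustration ranges from about 5% to 97% for the HOMA-IR group.

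**What to change.** In Section 3:

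1. For each distinct comparison, report rho with a 95% interval suited to Spearman (for example Fisher z with the Bonett-Wright standard error, or a bootstrap). Interpret size and interval rather than P<0.05 alone. Report HOMA-IR, ISI, FIRI and QUICKI as one comparison.
2. Mark in the results table which comparators share fasting insulin, 2-hour glucose or body weight/BMI with PREDIM, and define Belfiore's terms so that it can be placed. Do not count Raynaud, or the nearly equivalent fasting-insulin indices, as independent confirmation.
3. Check the printed PREDIM formula against its source, in particular the coefficient and sign of the fasting-insulin term. Then prespecify the expected sign of each correlation.
4. Limit the conclusion to concordance with surrogate indices in lean, normoglycaemic adults. Section 2.4 requires BMI below 25 and excludes, among others, "Glucose postprandial >140 mg/dL".

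Partial correlations given fasting insulin are not recommended. In an assumed model where PREDIM does track sensitivity, the median partial rho was about 0.28 for McAuley, 0.36 for Avignon and 0.40 for Stumvoll (the last two also given 2-hour glucose). At n = 25, plain Fisher z intervals around these are about -0.14 to 0.61, -0.06 to 0.67 and -0.01 to 0.70. All include zero, so a good index would look unsupported.

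The cost is a little more analysis of data already planned. The downside is wide intervals and a more modest claim.
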